6.3 Laboratory variables

More can be entered here

New variable	Rules
Coagulopathy	To be decided

6.4 Other variables

More can be entered here

STATISTICAL ANALYSIS PLAN

COPTIC: Coagulation and platelet laboratory testing in cardiac surgery
A prognostic study of associations between post-operative test results and subsequent bleeding

New variable	Rules
Age	(Operation date – DOB)/365.25
BMI	Weight (kg) / Height (cm) ² * 10,000
Time in theatre	Cumulative bypass time; cumulative cross-clamp time
Cardiac procedure	CABG, Valve, other (or combination)
Pre-operative kidney function	Pre-operative serum creatinine and dialysis information will be used to calculate estimated glomerular filtration rate (eGFR): Cockcroft-Gault formula: $eC_{Cr} = \frac{(140 - \text{Age}) \times \text{Mass (in kilograms)} \times [0.85 \text{ if Female}]}{72 \times \text{Serum Creatinine (in mg/dL)}}$ Or, when serum creatinine is measured in $\mu\text{mol/L}$: $eC_{Cr} = \frac{(140 - \text{Age}) \times \text{Mass (in kilograms)} \times \text{Constant}}{\text{Serum Creatinine (in } \mu\text{mol/L)}}$ where Constant is 1.23 for men and 1.04 for women.
Blood products as units	Divide volume (ml) by 280 to obtain red cells units Divide volume (ml) by 225 to obtain platelet units Divide volume (ml) by 260 to obtain FFP units Divide volume (ml) by 175 to obtain cryoprecipitate units Selected as averages of given NHSBT product specifications NB: Calculation of total units will be defined as missing if the total doses=0 and any of intra-op, grey area, INNOVIAN data are missing. i.e. they will not be recorded as missing if any doses given at any of these times is recorded, even if data at least one other time are missing.
Operative priority	This will be defined as “elective” or “urgent”. Any few emergency or salvage procedures will be classified as urgent.
Cardiac procedure	This will be classified in four groups; CABG only; CABG+valve; Valve alone; other
Involvement in other studies	An indicator will be created for each trial as follows: 
 (Y/N) for participation in HARVeST, PROMPT, VERDICT, Protection1 (n/liberal group/restrictive group) for TITRe2 (n/intervention group/control group) for PASPORT There will be no indicator for concurrent involvement in smaller trials.
Treatment group, time since withdrawal of dual anti-platelet therapy and cardiac procedure	These variables are to be combined. Any combination which included an “other” procedure was reviewed and classified according to whether or not the “other” procedure was considered to be the primary determinant of the risk of bleeding (from the point of view of the operation being done). Patients with an “other” procedure classified as being the determinant of bleeding became a new subset; all patients with an “other” procedure were reclassified according to their main procedure; for example “CABG and other” was reclassified as “CABG only.” If the only procedure was an “other” procedure judged to have a high bleeding risk, it was classified with the new “other” subset; if it was judged to have a low bleeding risk, e.g. ablation, the patient was excluded from the analysis population. The “other” procedures identified as having a high risk were K08 "Repair of double outlet ventricle

STATISTICAL ANALYSIS PLAN

COPTIC: Coagulation and platelet laboratory testing in cardiac surgery
A prognostic study of associations between post-operative test results and subsequent bleeding

New variable	Rules
	(Clean)", K33 "Aortic root replacement" and L19 "Other replacement of aneurysmal segment of aorta". The final categories will be as follows: 
- CABG only: no treatment- CABG+valve: no treatment- Valve only: no treatment- CABG only: aspirin- CABG+valve: aspirin- Valve only: aspirin- ABG only: dual_anti-platelet 0-2 days- ABG only: dual_anti-platelet 3-5 days- ABG only: dual_anti-platelet 6-7 days- CABG+valve: dual anti-platelet- Valve only: dual anti-platelet- Other: high risk

7. STATISTICAL ANALYSES

Statistical analyses and reporting will be undertaken in accordance with the STROBE (STrengthening the Reporting of OBservational studies in Epidemiology) guidelines [<http://www.strobe-statement.org/index.php?id=strobe-home>].

Initial laboratory parameters of interest are detailed in [section 2.6](#), although further investigations into other laboratory parameters not detailed here may be undertaken if there is evidence of potential associations with the primary and secondary outcomes based on the findings from these parameters. Laboratory parameters of interest will be examined individually, and within models where results are adjusted for each other laboratory parameter.

The distributions of the laboratory parameters of interest ([section 2.6](#)) will be compared between those defined as having CCB but this was only identified through one of the criterion ([section 5.1](#)) with those who were defined as CCB identified through two or more of the criteria. The main objective of this part of COPTIC Study B is to estimate the strength of associations between laboratory test results from the post-operative blood samples and CCB. Analysis will focus on estimating these associations, with sub-group analyses undertaken to examine the relationships between the timing of withdrawal of anti-platelet therapy and post-operative platelet function tests and primary and secondary outcomes.

Further details are as follows:

- A1: In all patients:
- a) characterise the distributions of the measurements from each laboratory test result;
 - b) fit regression models to estimate associations between the results of laboratory tests and the primary clinical outcome, CCB (see [section 5.1](#));
 - c) develop models that would be informative in predicting risk of CCB according to laboratory test results, both by consideration of these results as continuous

STATISTICAL ANALYSIS PLAN

COPTIC: Coagulation and platelet laboratory testing in cardiac surgery
A prognostic study of associations between post-operative test results and subsequent bleeding

measures or as above or below thresholds to be defined using receiver operating characteristic (ROC) analysis.

- A2: In the patient sub-groups *no anti-platelet drugs, aspirin alone* and *aspirin+ P2Y₁₂ blockers*:
- characterise the distributions of the measurements from each laboratory test;
 - fit regression models to estimate associations between the results of laboratory tests and the primary clinical outcome, CCB (see [section 5.1](#));
 - develop models that would be informative in predicting risk of CCB according to laboratory test results, both by consideration of these results as continuous measures or as above or below thresholds to be defined using receiver operating characteristic (ROC) analysis.
- A3: In the patient sub-group *aspirin+ P2Y₁₂ blockers*:
- characterise the distribution of time between withdrawal of P2Y₁₂ blocker prior to surgery and time of surgery;
 - fit regression models to estimate the association between the time of withdrawal of P2Y₁₂ blocker (either as a continuous or categorical variable) and the results of the primary laboratory tests (see [section 2.6](#)).
 - fit regression models to estimate the association between the duration of withdrawal of P2Y₁₂ blocker (either as a continuous or categorical variable) and CCB.

Initially the justification for the three separate subgroups would be sought by fitting models for the whole dataset and including interaction terms to formally test for differences between the groups.

The choice of fitting time of withdrawal as a continuous variable or as a category variable in b) and c) above will be based on the i) distribution of times (few discrete values or truly continuous), ii) the functional relationship between the time of withdrawal and the outcome (assessed using fractional polynomials) and iii) interpretability of the findings.

- A4: In all patients:
- fit separate regression models to estimate associations between the results of laboratory tests and the secondary outcomes (see [section 5.2](#));
 - develop models that would be informative in predicting risk of each secondary outcome according to laboratory test results, both by consideration of these results as continuous measures or as above or below thresholds to be defined using receiver operating characteristic (ROC) analysis.

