2.6.1 Primary laboratory predictors (test results considered likely to predict CCB)

Test result	Laboratory test and platform	Likely predictor of CCB
Platelet count	FBC (XE-2100 cell counter)	LOW test result
Multiplate ADP test AUC	Multiplate	LOW test result
Multiplate AA test AUC	Multiplate	LOW test result
Multiplate TRAP test AUC	Multiplate	LOW test result
Multiplate ADR test AUC	Multiplate	LOW test result
ROTEM intem CT	ROTEM	HIGH test result
ROTEM intem alpha	ROTEM	LOW test result
ROTEM intem mcf	ROTEM	LOW test result
ROTEM intem ml	ROTEM	HIGH test result
ROTEM intem maxV	ROTEM	LOW test result
ROTEM intem maxV-t	ROTEM	HIGH test result
ROTEM extem CT	ROTEM	HIGH test result
ROTEM extem alpha	ROTEM	LOW test result
ROTEM extem mcf	ROTEM	LOW test result

STATISTICAL ANALYSIS PLAN

COPTIC: Coagulation and platelet laboratory testing in cardiac surgery
A prognostic study of associations between post-operative test results and subsequent bleeding

ROTEM extem ml	ROTEM	HIGH test result
ROTEM extem a10	ROTEM	LOW test result
ROTEM extem maxV	ROTEM	LOW test result
ROTEM extem maxV-t	ROTEM	HIGH test result
ROTEM fibtem mcf	ROTEM	LOW test result
ROTEM fibtem a10	ROTEM	LOW test result
ROTEM extem mcf - fibtem mcf	ROTEM	LOW test result
ROTEM intem CT - heptem CT	ROTEM	HIGH test result
TEG CK rmin	TEG	HIGH test result
TEG CK angledeg	TEG	LOW test result
TEG CK ma	TEG	LOW test result
TEG CK ly60	TEG	HIGH test result
TEG CK rmin – CKH rmin	TEG	HIGH test result

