3.1 Sample size

The study sample size detailed in the protocol (version 6, 21 March 2012) is 2400 which corresponds to the entire predicted patient throughput at Bristol Heart Institute for the 2 year study period, allowing for up to 10% of patients to opt-out.

Details regarding the sample size calculation and review are given in the SAP covering analyses of pre-operative test results.

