7.4.3 Analysis models

All outcomes listed in the study protocol will be presented as per the template tables [Table T7 to T8](#). General methods of presentation are outlined below.

⁷ i.e. factors associated with the both the laboratory test result(s) (exposure) and the outcome, unbalanced across the groups and not an intermediary step in the causal pathway from the exposure to outcome

The primary outcome (CCB) and secondary outcomes (any RBC transfusions > 4 units RBC transfusion, non-routine pro-haemostatic treatments, death, MI, any stroke, renal failure, AKI and infections during hospital admission) are all binary data.

These binary outcomes will be presented as numbers and percentages of patients. The association between laboratory test results and outcome will be quantified using logistic regression for binary data. Estimates will be presented as unadjusted and adjusted odds ratios (OR) and 95% confidence intervals (95% CI). For these binary outcomes analyses will only be performed if more than ten patients in total experience the outcome.

The sensitivity and specificity of laboratory test results to predict the outcome will be described for different thresholds and laboratory tests will be compared using the area under the receiver operating characteristic (ROC) curve.

The association between time of withdrawal of P2Y₁₂ blocker and laboratory test results will be described using linear regression.

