7.4.4 Statistical significance

For hypothesis tests and tests of interactions, two-tailed p-values < 0.05 are considered statistically significant. Likelihood ratio tests will be used in preference to Wald tests for hypothesis testing.

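### Thresholds chosen by ROC analysis are then modelled in the same patients with ordinary odds ratios, confidence intervals and p<0.05, so the threshold versions in A1(c), A2 and A4 are optimistic

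*SAP*

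**What the plan says.** SAP section 7, item A1(c), plans prediction models for CCB in all patients. The laboratory results are considered both as continuous values and as dichotomies, the latter at cut-offs still to be found: "measures or as above or below thresholds to be defined using receiver operating characteristic (ROC) analysis". A2 repeats this for the three anti-platelet subgroups and A4 for each secondary outcome ("continuous measures or as above or below thresholds to be defined using receiver operating characteristic (ROC) analysis"). No ROC criterion is named.

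For binary outcomes, section 7.4.3 specifies logistic regression: "Estimates will be presented as unadjusted and adjusted odds ratios (OR) and 95% confidence intervals (95% CI"). It also says that sensitivity and specificity will be described at different thresholds and that tests will be compared by area under the curve. Section 7.4.4 adds that "two-tailed p-values < 0.05 are considered statistically significant" and that "Likelihood ratio tests will be used in preference to Wald tests for hypothesis testing". Neither section makes an exception for a term whose cut-off came from the data.

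Section 7.4.10 says that formal adjustment may be needed for the number of tests. It does not deal with the search for a cut-off within one test.

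The detailed model fitting in 7.3 (models 2A–2E) uses fractional polynomials and backward elimination and mentions no dichotomised term.

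**The concern.** An ROC cut-off is found by looking at the outcome. The 1-df likelihood ratio reference and the ordinary confidence interval assume a cut-off fixed beforehand. If the same patients supply the cut-off and then test it, the search goes unaccounted for. An unrelated test is declared a predictor more often than 5%, its odds ratio moves away from 1, and its sensitivity and specificity look better than they would in new patients.

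The search is planned for many tests (27 in the list headed "Primary laboratory predictors (test results considered likely to predict CCB"), in three drug subgroups and for several outcomes. Section 7.4.3 sets a low floor for events: "analyses will only be performed if more than ten patients in total experience the outcome". A cut-off is also the result that a clinician could most readily take from the paper.

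**Working it through.** **Inputs from the SAP.** Two-tailed level 0.05 and likelihood ratio tests (7.4.4). Planned size: "The study sample size detailed in the protocol (version 6, 21 March 2012) is 2400" (3.1). Dual therapy in about 25% of patients (2.3), so 0.25 × 2400 = 600 in that subgroup. A direction (LOW or HIGH) for each primary predictor (2.6.1). Baseline score forced in with coefficient 1.00 (7.3).

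**Assumptions.** The CCB rate is not in the SAP; 10%, 30% and 45% were used. The ROC rule is not in the SAP; two common ones were used:

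- Youden: maximise J = sensitivity + specificity − 1.
- Closest to corner: minimise (1 − sensitivity)² + (1 − specificity)².

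**Method.** Simulate a test result independent of CCB, choose the cut-off by the rule, then compute G = 2 Σ O ln(O/E) on the resulting 2×2 table in the same patients and reject if G > 3.84. There were 2000 runs per setting with N = 600, 1200 and 2400.

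**The plan's own level first.** With the cut preset at the median, rejection was 0.036–0.068 across the unadjusted settings and 0.052 in a logistic model with the baseline score as offset (N = 2400, 1500 runs). The nominal 0.05 is therefore reproduced when nothing is searched.

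**With the cut-off chosen in the same patients:**

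| Rule | Direction | Rejection at nominal 0.05 | Divided by 0.05 |
|---|---|---|---|
| Youden | pre-listed | 0.245–0.273 | 4.9–5.5 |
| Youden | either | 0.419–0.448 | 8.4–9.0 |
| Closest to corner | pre-listed | 0.074–0.098 | 1.5–2.0 |
| Closest to corner | either | 0.143–0.208 | 2.9–4.2 |
| Youden, 20–100 distinct values (N = 2400, 30% CCB) | pre-listed | 0.142–0.209 | 2.8–4.2 |
| Youden, 20–100 distinct values (N = 2400, 30% CCB) | either | 0.286–0.378 | 5.7–7.6 |

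A repeat simulation gave 26–30% (Youden, pre-listed), 43–46% (Youden, either) and 8–10% (closest to corner, pre-listed), against 5–6% for a preset median cut.

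**Large-sample check of the Youden figure.** For a cut leaving a fraction q of patients on the adverse side and CCB rate π, the Pearson statistic is N J² π(1 − π) / [q(1 − q)]. Under no association, √(N π(1 − π)) × J, as the cut moves, behaves as a Brownian bridge. At its maximum, the squared height divided by q(1 − q) has a chi-square distribution on 3 df, not 1. Hence P(χ²₃ > 3.84) = 0.050 + √(2 × 3.84/π₀) × e^(−1.92) = 0.050 + 0.229 = 0.279, with π₀ = 3.1416. This agrees with the simulation and does not involve N or the CCB rate, which explains why neither matters much.

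**Isolating the cause.** Same offset model, unrelated test, N = 2400: Youden (either direction) found and tested in the same patients 0.411; cut-off found in one half and tested in the other 0.047; cut-off fixed in advance 0.052; continuous term 0.052.

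**Optimism in the estimates.** With no true association (odds ratio 1.00), the median odds ratio at the Youden cut in the pre-listed direction was 1.17–1.30 at N = 2400 and 1.36–1.65 at N = 600. With a true shift of 0.2 SD and 25% CCB, sensitivity + specificity was over-stated by about 0.02 at N = 2400 and 0.05 at N = 600, and the odds ratio by about 11% and 28%.

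**The case against.** The strongest reply is that the SAP never says in so many words that an ROC-derived binary term will be declared significant. A1(b) is the association analysis and A1(c) is model development. The level in 7.4.4 is generic, and where 7.4.3 mentions thresholds it describes sensitivity and specificity at several of them. This stands in part: description over several thresholds, and comparison by area under the curve, need no correction. But A1(c), A2 and A4 put dichotomised results into models, and the odds ratios, intervals and tests of 7.4.3–7.4.4 are the only ones the SAP provides. That the cut-off and the model use the same patients is likewise an inference, drawn from the absence of any other sample.

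Second, the primary predictors were listed because they are thought likely to predict CCB, so a pure null is not the typical case, and at full size the over-statement of sensitivity + specificity is only about 0.02. Subgroup models also depend on interaction tests first. This limits the practical size in all patients. It does not repair the intervals or the smaller groups.

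Three stronger readings are tempting and are not supported:

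- That the whole analysis is affected. Continuous terms are planned beside the thresholds, and models 2A–2E use fractional polynomials.
- That the error is five times nominal as a fact. That holds for Youden, a continuous result and the pre-listed direction; the SAP names no rule.
- That the statistic tested is the largest over all cut-offs. A Youden cut-off maximises J, and the formula above shows that this does not maximise the test statistic, because q(1 − q) changes with the cut.

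**Conclusion.** The concern holds for the threshold versions of the models in A1(c), A2 and A4, and only for those. Followed as written, they give p-values and intervals that ignore the cut-off search. For an unrelated result the nominal 5% becomes about 25–30% (Youden, pre-listed direction), 7–10% (closest to corner, pre-listed direction) or up to about 45% (Youden, either direction), which is roughly 1.5 to 9 times nominal. Every rule examined exceeded 5%. The width of the range comes from the unnamed ROC rule.

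The figures assume independent patients, CCB rates of 10–45% for the error rates, and results without ties except where stated. The accuracy and odds-ratio optimism under a true effect assumes a 0.2 SD shift, 25% CCB and Youden; it is modest at 2400 patients and more than twice as large at 600.

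**What to change.** In A1(c), A2 and A4:

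- Base every odds ratio, confidence interval and p-value on the continuous or fractional-polynomial term, as 7.3 already does for the platform models.
- Name one ROC cut-off rule, and the direction of search, in advance.
- Use thresholds only to describe sensitivity and specificity, and correct these with a bootstrap that repeats the cut-off search in each resample.
- If a p-value for a threshold is reported, obtain it by permuting CCB (or the secondary outcome concerned) and repeating the search in each permutation.

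One sentence in 7.4.10 should separate this from adjustment for the number of tests. The cost is SAP wording and some extra computing, with no new data. The downside is that the reported threshold performance will look slightly less favourable.

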7.1 A priori expected relationships

For each patient characteristic, the following are likely to be associated with an INCREASED likelihood of CCB.

- Increased age
- Female
- Diabetes yes
- Other>CABG+valve>Valve>CABG

5. Urgent operative priority>elective
6. Decreased eGFR
7. Decreased preoperative HCT
8. Low preoperative platelet count
9. Aspirin+P2Y12 blocker (clopidogrel or prasugrel) >aspirin>no drugs
10. Decreased time from P2Y12 blocker withdrawal
11. Reduced BMI

7.2 Specific analysis procedure

The approach is to evaluate the separate platforms (Multiplate/preop; ROTEM; TEG; Multiplate/postop) individually in the first instance, and then evaluate whether the inclusion of additional platforms would improve this. The reason for considering groups of variables by platform (rather than simply choosing the 'best' subset of variables) is because there is no cost of using extra variables from one platform, but an extra cost of doing a second test. The specific steps are as follows:

- Step 1 Review the prediction achieved by patient characteristics. Define an optimal model based only on "baseline" covariates⁶. There will be a separate model for
- **any CCB** (intra-operative or post-operative) and
 - **post-op CCB** only
- Comment: We expect these models to be consistent with one another, not least because the majority of events (post-op CCPB events) will be common to both models.*
- Step 2 Review of each test platform to obtain the best model for each, including the baseline covariates:
- pre-operative Multiplate in relation to **any CCB** (this model is interesting in its own right, but from a slightly different perspective, i.e. it allows the care team to make a plan to mitigate the risk of CCB or to prepare to manage it)
 - pre-operative Multiplate in relation to **post-op CCB**
 - post-operative Multiplate in relation to **post-op CCB**
 - post-operative ROTEM in relation to **post-op CCB**
 - post-operative TEG in relation to **post-op CCB**
- Comment: Each of these models will consider all variables for the test/timepoint, i.e. consider the test/timepoint as a "package." The first model stands alone for **any CCB**. For **post-op CCB**, this step will identify which of the latter four models is the best platform for predicting CCB, i.e. provides the best prediction. We hypothesise that the best platform will be one of the post-op platforms because the information from these is more 'proximal' to the outcome for these models, i.e. **post-op CCB**.*
- For the best test/timepoint** (assuming there is one best test), we will also investigate whether a model using test variables that are available early (for the test identified as best) performs as well as a model using the standard test variables available at "test completion."

⁶ These are: age, sex, diabetic status (n/y), cardiac procedure (CABG only, CABG + valve, valve alone, other), operative priority (elective, urgent), eGFR, preoperative HCT, treatment group, time since withdrawal (anti-platelet group), body mass index (BMI), preoperative platelet function and participation in another clinical study.

- Step 3 Test whether the addition of one of the other (post-operative) platforms improves this best model for **post-op CCB**. In practice, this is likely to be a test of whether Multiplate-post improves prediction compared to either ROTEM or TEG (or, adding ROTEM or TEG to Multiplate-post, since ROTEM and TEG are assessing similar mechanisms and Multiplate is assessing different ones). The combination of ROTEM and TEG together will not be considered.
- For the test/timepoint** added at Step 3 (assuming that there is one), we will also investigate whether a model using test variables that are available early (for the test/timepoint added at Step 3) performs as well as a model using the standard test variables available at “test completion.”
- Step 4 Test whether the addition of the pre-operative Multiplate platform improves the model identified in Stage 3.
- If Multiplate-pre** is added at Step 4, we will also investigate whether a model using test variables that are available early for Multiplate-pre performs as well as a model using the standard test variables available at “test completion.”

